- a. The screening visit is to occur within 35 days of randomization (day 1 [visit 2]). Subjects will record daily VMS during the screening period in an electronic diary. To qualify for the study, within 10 days prior to randomization, subject must have a minimum average of 7 to 8 moderate to severe hot flashes (VMS) recorded per day, or 50 to 60 per week. History of average caffeinated beverage intake will be collected at baseline. At each clinic visit, the caffeinated beverage intake within the past 24 hours will be recorded. Subjects may be retested 1 time for assessments upon approval of the medical monitor. Subjects may be rescreened up to 1 time, upon the approval of the medical monitor. Subjects may not rescreen if the VMS eligibility report has been run. The following assessments do not need to be repeated at the rescreen provided they still fall within the acceptable procedure completed time frame window: TVU, endometrial biopsy, mammogram, ECG and Pap test (or equivalent cervical cytology).
- b. The follow-up visit (visit 16) will occur approximately 3 weeks following the last dose of study drug.
- c. Subjects will return to the study site for visits and procedures to occur within ± 3 days of the scheduled day. Unscheduled visits can be planned outside the scheduled visits.
- d. Signed informed consent will be collected for all subjects before any study-related procedures are done. Subjects who do not consent to PGx sampling are not excluded from participating in the study.
- e. ePRO assessments will be self-administered at the study site first upon arrival and before any other study assessments/procedures are performed; assessments at visit 2 must occur prior to randomization/first dosing; assessments at all other visits must occur prior to dosing. In the event a subject withdraws from the study, efforts to collect information on the site-based ePRO measures should be made before or shortly after discontinuation. The assessments will be administered electronically via the site tablet on day 1, week 4, week 12, week 24 and week 52.
- f. A clinician will administer the C-SSRS measure electronically at the clinic visit, prior to any invasive procedures. This will be administered at screening (visit 1), day 1 (visit 2), week 12 (visit 5), week 24 (visit 8), week 52 (visit 15) and the follow-up visit (week 55 [visit 16]).

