5.5.6 Follow-up of Adverse Events

All AEs occurring during or after the subject has discontinued the study are to be followed up until resolved or judged to be no longer clinically significant, or until they become chronic to the extent that they can be fully characterized by the investigator.

If after the protocol defined AE collection period [see Section 5.5.1 Definition of Adverse Events], an AE progresses to a SAE, or the investigator learns of any (S)AE including death,

where he/she considers there is reasonable possibility it is related to the study drug treatment or study participation, the investigator must promptly notify the sponsor.

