- ALT or AST $> 3 \times$ ULN and TBL $> 2 \times$ ULN or INR > 1.5
- ALT or AST $> 3 \times$ ULN with the appearance of fatigue, nausea, vomiting, right upper quadrant pain or tenderness, fever, rash and/or eosinophilia ($> 5\%$ increase above baseline)

Subjects who develop a signal of liver injury will be monitored every 2 to 4 weeks if the study drug is discontinued. If the subject remains on study drug, they will be closely monitored for liver biochemistry results. Subjects with a signal of elevated transaminases ($> 3 \times$ ULN) will have a pre-dose PK sample drawn in addition to repeat blood draws for liver biochemistry monitoring. These samples can be held for potential analysis based on the subject’s clinical outcome.

In addition, if close monitoring for a subject with moderate or severe hepatic laboratory tests is not possible, study treatment should be discontinued.

*Hy's Law Definition: Drug-induced jaundice caused by hepatocellular injury, without a significant obstructive component, has a high rate of bad outcomes, from 10 to 50% mortality (or transplant).

The 2 "requirements" for Hy's Law are:

1. Evidence that a drug can cause hepatocellular-type injury, generally shown by an increase in transaminase elevations higher $3 \times \text{ULN}$ (" $2 \times \text{ULN}$ elevations are too common in treated and untreated patients to be discriminating").
2. Cases of increased bilirubin (at least $2 \times \text{ULN}$) with concurrent transaminase elevations at least $3 \times \text{ULN}$ and no evidence of intra- or extra-hepatic bilirubin obstruction (elevated ALP) or Gilbert's syndrome [Temple, 2006].

FDA Guidance for Industry, "Drug-Induced Liver Injury: Premarketing Clinical Evaluation," 2009:

1. The drug causes hepatocellular injury, generally shown by a higher incidence of 3-fold or greater elevations above the ULN of ALT or AST than the (nonhepatotoxic) control drug or placebo.
2. Among study subjects showing such AT elevations, often with ATs much greater than $3 \times \text{ULN}$, 1 or more also show elevation of serum TBL to $> 2 \times \text{ULN}$, without initial findings of cholestasis (elevated serum ALP).
3. No other reason can be found to explain the combination of increased AT and TBL, such as viral hepatitis A, B or C; preexisting or acute liver disease; or another drug capable of causing the observed injury.

References

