6.5.2 Clinical Laboratory Evaluation

Quantitative values evaluated by the central laboratory including hematology, biochemistry, and urinalysis will be summarized using mean, standard deviation, minimum, maximum and median by treatment group at each analysis visit. Additionally, a within-subject change will be calculated as the post-baseline measurement minus the baseline measurement and summarized in the same way. Each laboratory result will be classified as low (L), normal (N), or high (H) at each visit according to the laboratory supplied reference ranges.

The number and percentage of subjects below and above reference range will be summarized for each treatment group at each visit.

Number and percentage of subjects with platelets $< 150000/\mu$ L ($150,000/\mu$ L ($150 \times 10^9/L$) will also be summarized.

Frequency tabulations of qualitative clinical laboratory variables (urinalysis) will be presented for each treatment group at each visit.

For hematology and biochemistry shift tables will be presented for each treatment group:

• Summary shifts of reference range changes from baseline to worst finding during the treatment period (shift from normal or high to low, shift from normal or low to high, categorized increase [shift from low to normal or from normal to high], categorized no change [value stays in the same reference range], categorized decrease [shift from high to normal or from normal to low]).

For hormone related parameters, if the value is below the low limit of quantification, the value will be imputed as half of the LLOQ. In addition, the percentage of subjects who have BLOQ values at baseline who then have measurable post-baseline values will be summarized.

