| Target day | Analysis window | Analysis visit |
|------------|---|----------------|
| D1 | last non-missing value on or prior to day 1 | Baseline |
| D29 | FD22 to FD36 | Week 4 |
| D85 | FD72 to FD 92 | Week 12 |
| D113 | FD106 to FD120 | Week 16 |
| D141 | FD134 to FD148 | Week 20 |
| D169 | FD162 to FD176 | Week 24 |
| D197 | FD190 to FD204 | Week 28 |
| D225 | FD218 to FD232 | Week 32 |
| D253 | FD246 to FD 260 | Week 36 |
| D281 | FD274 to FD288 | Week 40 |
| D309 | FD302 to FD316 | Week 44 |
| D337 | FD330 to FD344 | Week 48 |
| D365 | FD358 to FD372 | Week 52 |

The VMS efficacy windows are smaller because they are calculated from daily data and are not dependent on the scheduling of visits. The non-VMS efficacy endpoint are not collected during the follow-up period.

If more than one observation exists within the analysis window, the observation closest to the scheduled visit day will be selected for that visit. If there are two observations that have the same distance from the scheduled day, the value that is before the scheduled day will be selected in the analysis. If more than one observation is made on the same day, an average value if continuous, or the worst value if categorical, will be included in the analysis.

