6.10.1.2 Safety Analysis Windows

Except for adverse events, for the analysis window, the last day is always 1 day after the last day of exposure to overall study treatment.

The end of overall treatment is defined as the last day of treatment (e.g., discontinued study or entered follow-up period) +1 and the follow-up period for analysis windows begins at last overall treatment + 2 days and onward (Follow-up Study Day 2).

| Analysis | Scheduled | Analysis Windows (Fezolinetant day) | | | |
|-----------|--------------------|-------------------------------------|----------------------|---------------------|-----------------|
| Visits | Day in Protocol | a) | b) | c) | d) |
| Baseline | Day 1 | Last non-missin | ng value on or prior | to fezolinetant day | y 1 (inclusive) |
| Week 2 | Day 15 | 2 to 22 | | | |
| Week 4 | Day 29 | 23 to 43 | 2 to 43 | 2 to 57 | |
| Week 8 | Day 57 | 44 to 71 | 44 to 71 | | |
| Week 12* | Day 85 | 72 to 92 | 72 to 99 | 58 to 99 | 2 to 127 |
| Week 14 | D99 | 93 to 106 | | | |
| Week 16 | D113 | 100 to 127 | 100 to 127 | 100 to 127 | |
| Week 20 | D141 | 128 to 155 | 128 to 155 | 128 to 155 | |
| Week 24 | D169 | 156 to 183 | 156 to 183 | 156 to 183 | 128 to 267 |
| Week 28 | D197 | 184 to 211 | 184 to 211 | 184 to 211 | |
| Week 32 | D225 | 212 to 239 | 212 to 239 | 212 to 239 | |
| Week 36 | D253 | 240 to 267 | 240 to 267 | 240 to 267 | |
| Week 40 | D281 | 268 to 295 | 268 to 295 | 268 to 295 | |
| Week 44 | D309 | 296 to 323 | 296 to 323 | 296 to 323 | |
| Week 48 | D337 | 324 to 351 | 324 to 351 | 324 to 351 | |
| Week 52** | D365 | 352 to 376 | 352 to 376 | 352 to 376 | 268 to 376 |
| Week 55 | D386 | Last non-missin | ng follow-up day | | |

The data summary by visits will be done following the analysis windows specified in the table below:

a) Apply to liver biochemistry and INR testing

- b) Apply to complete Clinical laboratory and urinalysis, Vital signs
- c) Apply to Blood PD/PK sample, including hormones (PD only at Week 55)
- d) C-SSRS

*The analysis window for the Week 12 ECG assessment (Target Day 85) is FDay 2 through FDay 99

**The analysis window for the Week 52 ECG is last non-missing day from FDay 100 to FUD1; The analysis window for the Week 52 bone marker is FDay 2 to FUD1; The analysis window for the Week 52 TVU and biopsy assessments is FDay 2 until last treatment + 30 days.

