If more than one observation exists within the analysis window, the same rules will be followed as described above for efficacy analysis visit windows, except that if there are two observations that have the same distance from the scheduled day, the value that is after the scheduled day will be selected in the analysis.

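### The Week 55 safety row in the 52-week SAP takes the last follow-up value with no day limit, so where abnormality-driven repeats enter the data it tends to show recovered values, chiefly for liver tests

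*SAP*

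**What the plan says.** The 52-week SAP, Section 6.10.1.2, lists safety analysis visits with day ranges. Week 55 (scheduled Day 386) has none; its entry is "Last non-missin | ng follow-up day". The same section starts the follow-up period at FUD2 and gives it no end.

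For a window holding several values, the safety section refers to the efficacy rule in Section 6.10.1.1: "the observation closest to the scheduled visit day will be selected for that visit". It changes only the tie-break: with two equidistant values, "the value that is after the scheduled day will be selected in the analysis".

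The protocol schedules one follow-up contact (Table 1, footnote b): "The follow-up visit (visit 16) will occur approximately 3 weeks following the last dose of study drug", with a visit window of ±3 days.

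The row feeds the by-visit laboratory summaries of Section 6.5.2, which include means, changes from baseline and this tabulation: "The number and percentage of subjects below and above reference range will be summarized for each treatment group at each visit".

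Two protocol sections bear on who is sampled again:
- Appendix 12.4, liver monitoring: "Subjects who develop a signal of liver injury will be monitored every 2 to 4 weeks if the study drug is discontinued".
- Section 5.5.6, adverse events: "All AEs occurring during or after the subject has discontinued the study are to be followed up until resolved". The sentence goes on to two other endpoints: loss of clinical significance, or becoming chronic.

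**The concern.** A row labelled Week 55 should describe subjects about 3 weeks after the last dose. Under a last-value rule, the sample that fills it depends on when each subject's sampling stopped. A subject who is normal at Visit 16 usually has no later sample, so her 3-week value stands. A subject who is abnormal there, and is repeated, has that value replaced by a later one. The choice of sample is therefore linked to the result being summarised.

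At stake is the planned by-visit picture of laboratory values after stopping. The other laboratory summaries do not supply it. The liver highest-value table (Section 6.5.2.1) ends at last dose + 1 day, and the shift tables (Section 6.5.2) use the worst finding during treatment. The time point has some relevance: Protocol Section 1.5 reports transaminase increases during follow-up in 2 phase 2b subjects.

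**Working it through.** There is no planned figure to reproduce, because the issue is a record-selection rule. The check has four steps.

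**1. Timing.** From the schedule, 386 − 365 = 21 days, so Week 55 is meant as FUD21. With ±3 days the visit falls on FUD18 to FUD24. If the last dose is on Day 364, the target is 386 − 364 = 22 and the span is FUD19 to FUD25.

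**2. Selection rules in the 52-week SAP, side by side.**

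| Row | Day range | Value taken |
|---|---|---|
| Numbered on-treatment laboratory windows | Bounded | Nearest scheduled day, ties to the later value |
| Diary Week 55 (6.10.1.1) | FUD15 to FUD21 | Average over the week |
| Safety Week 55 (6.10.1.2) | FUD2 onward, no end | Last available |

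The nearest-day rule does not rescue the safety row. It chooses among values inside a window, whereas this row's definition already names one day, the last.

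**3. Who has samples after Visit 16.**
- Protocol Section 5.4.3 allows abnormal tests to be repeated when clinically indicated.
- Section 5.5.1.1 makes clinically significant findings reportable as adverse events, and Section 5.5.6 follows these, including after the subject leaves the study.
- Appendix 12.4 calls for repeats of moderate liver abnormalities two or three times a week, tapering later, and for continued monitoring after drug is stopped for a liver signal.

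All three routes start from an abnormal or suspect result. None adds late samples for subjects who were normal. Hormone samples and the C-SSRS have no comparable repeat loop.

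**4. Direction and possible size.** Let p be the share abnormal at the scheduled visit, r the share of those with a later repeat in the analysis data, and q the share of those repeated who are normal at the last repeat. If nobody normal at the visit is later recorded as abnormal:

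share abnormal under the last-value rule = p × (1 − r × q), which cannot exceed p.

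The documents give no value for p, r or q. The following are assumptions, to show the range:

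| p | r = 0 | r = 0.5, q = 0.5 | r = 0.5, q = 1 | r = 1, q = 0.5 | r = 1, q = 1 |
|---|---|---|---|---|---|
| 5% | 5.0% | 3.75% | 2.5% | 2.5% | 0% |
| 2% | 2.0% | 1.5% | 1.0% | 1.0% | 0% |

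For one subject with an assumed series of 4.2, 3.4, 2.1 and 0.9 × ULN at FUD21, 24, 28 and 42, the row as written takes 0.9. The value nearest FUD21 is 4.2.

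The rule can also err early. If Visit 16 is missed and the only follow-up sample is at FUD5, that sample becomes Week 55.

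**The case against.** Several points on the other side stand and limit the claim.

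- **Last-value rules appear elsewhere in this SAP.** Baseline and the Week 52 ECG also use one. The contrast is with the numbered on-treatment laboratory windows and the diary Week 55 window, not with every other visit.
- **Re-testing until recovery is not universal.** A reader might infer that every abnormality followed to resolution is shown as normal, so that the row counts only those that never resolved. The protocol does not support this. Repeats of general tests are optional, only clinically significant findings become adverse events, and their follow-up can end with the finding chronic. The mechanism is firm for liver signals and clinically significant findings, not for ordinary out-of-range values.
- **Later samples must be in the analysis data.** Section 6.5 exempts follow-up visit data from the last dose + 1 day cut-off. If that means Visit 16 alone, later repeats are excluded and most of the effect goes. Section 6.10.1.2, however, speaks of a follow-up day and excludes no repeats. Section 6.5.2 summarises central-laboratory values, so local repeats would not enter.
- **The phase 2b cases are weak support.** Protocol Section 2.2.2 describes one elevation found at the 3-week follow-up visit, after normal values throughout, and considered unlikely to be related to study drug. It shows that the time point can matter, not that a drug effect was seen there.
- **Other outputs capture much of this.** A reader might infer that post-treatment signals would be hidden. They would not: treatment-emergent events run to 21 days after last dose, liver test elevations and thrombocytopenia are events of special interest, severe liver abnormalities without another cause are reported as serious, and laboratory data are listed. The backstop is partial, because a Visit 16 result at FUD22 to FUD24 falls after the 21-day limit and not every abnormal value becomes an adverse event.

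**Conclusion.** The concern holds in a limited form. As written, the Week 55 safety row depends on when sampling ended, and later sampling is driven mainly by abnormality. Where those repeats are in the analysis data, the row leans towards recovered values, chiefly for liver tests, and does not reliably describe status about 3 weeks after the last dose.

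The size is unknown. It runs from nil (no eligible repeats) to loss of every 3-week abnormality (all repeated and all normal at the last repeat). A value that worsens late would push the other way, but because abnormality triggers the repeats, the expected net direction is downward. All 52-week summaries are descriptive, so no test, error rate or efficacy result changes. The change is worth making because it is cheap and no other planned by-visit laboratory summary covers this period.

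**What to change.** In the 52-week SAP, Section 6.10.1.2, replace the Week 55 entry with the value nearest FUD21 within a bounded follow-up window, keeping the existing tie-break. FUD14 to FUD28 is one option; any window should cover at least FUD18 to FUD24. State the target in follow-up days, because Day 386 does not correspond to 3 weeks after last dose for early discontinuers or, counted in fezolinetant days, for subjects switched from placebo. Say whether unscheduled repeats are eligible, and list all follow-up samples outside the window.

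Optionally, add a summary of the worst follow-up value (FUD2 onward) for liver tests and platelets. This answers a related gap: the liver highest-value table stops at last dose + 1 day.

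The cost is one table entry and a small programming change; the optional summary adds one short table. The downside is that a few very early or very late follow-up visits drop out of the row and appear only in listings. Section 1 places approval of the updated SAP before final database lock, so the change belongs there. After that it would have to be documented and justified in the clinical study report.

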5 ENDPOINTS

The calculation of efficacy baseline for VMS frequency and severity is described in the 12-week analysis SAP, and will be calculated based on the number of moderate to severe hot flashes in the 10 days immediately prior to randomization.

For general efficacy endpoints collected at visits, the last non-missing assessment on or prior to the first dose of study treatment (investigational product or placebo) is the baseline.

For all general safety endpoints, in contrast, the baseline value will be the last non-missing value taken on or prior to first dose of fezolinetant.

Note that the baseline calculations differ between efficacy and safety analyses. The efficacy endpoints are subjective and there is expected to be a non-ignorable placebo effect, so the entire double-blind portion of the study is considered post-baseline for all subjects. For safety endpoints, any changes while on placebo during the double-blind portion of the study are expected to be within-subject variation and changes from baseline will be assessed beginning with exposure to fezolinetant.

The table below provides additional details regarding the baselines for specific endpoints. The terms R_{BL} and $WK12_{BL}$ indicate where the baseline is established, where R_{BL} is initial randomization and $WK12_{BL}$ is the start of the extension period at Week 12.

| Endpoint | Baseline | | |
|--|-----------------|-----------------|--|
| - | fezolinetant / | placebo / | |
| | fezolinetant | fezolinetant | |
| General efficacy | R _{BL} | R _{BL} | |
| General safety and TVU | R _{BL} | $WK12_{BL}$ | |
| Hormones | R _{BL} | $WK12_{BL}$ | |
| Demographics | R _{BL} | R_{BL} | |
| Medical history | R _{BL} | R _{BL} | |
| Prior medications | R _{BL} | $WK12_{BL}$ | |
| Concomitant medications | R _{BL} | $WK12_{BL}$ | |
| Study drug exposure and compliance | R _{BL} | $WK12_{BL}$ | |
| TEAE | R _{BL} | $WK12_{BL}$ | |
| Clinical lab summary shifts and liver safety assessments | R _{BL} | $WK12_{BL}$ | |
| Protocol deviations | R _{BL} | R _{BL} | |
| Biopsy (Listing only) | R _{BL} | R _{BL} | |

The 12-week double-blind placebo period will be completely described as part of the treatment comparisons within the 12-week double-blind analyses. As a result, all endpoints in the 52-week analysis are from the first dose of fezolinetant and onward (see Section 6.10 for additional details).

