6.10.1 Analysis Windows

Study Day for analysis windows during the double-blind treatment phase will be calculated as date of visit/assessment – first dose date +1.

Study Day during the extension phase will be calculated as date of visit/assessment – first dose date of the extension phase +1.

Study Day for the follow-up (FUD) phase will be calculated as date of visit/assessment – last dose date of study treatment (Date of EOT).

Fezolinetant Study Day (FD) will be calculated as date of visit/assessment – first dose date of fezolinetant +1. Note that this is the same as Study Day for subjects randomized to fezolinetant in the double-blind treatment phase. Post-baseline data prior to first dose of fezolinetant Day 1 is excluded from the analyses described in this SAP unless otherwise noted.

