6.10.1.1 Efficacy Analysis Windows

For the analysis windows, the last day is always the last day of exposure to overall study treatment. For VMS diary data the last day of exposure includes events reported until

8:00AM the following day. For example, the Week 1 average will include diary data from 8AM on Day 1 through 7:59AM on Day 8.

For both VMS and non-VMS efficacy, the end of overall treatment is defined as the last day of treatment (e.g., discontinued study or entered follow-up period) and the follow-up period begins at last overall treatment + 1 day.

| Analysis study week | Analysis window |
|---------------------|--|
| Baseline | Non-missing days from D-10 up to and including D-1 |
| Week 1 | FD1 to FD7 |
| Week 2 | FD8 to FD14 |
| Week 3 | FD15 to FD21 |
| Week 4 | FD22 to FD28 |
| Week 5 | FD29 to FD35 |
| Week 6 | FD36 to FD42 |
| Week 7 | FD43 to FD49 |
| Week 8 | FD50 to FD56 |
| Week 9 | FD57 to FD63 |
| Week 10 | FD64 to FD70 |
| Week 11 | FD71 to FD77 |
| Week 12 | FD78 to FD84 |
| Week 16 | FD110 to FD116 |
| Week 20 | FD138 to FD144 |
| Week 24 | FD166 to FD172 |
| Week 28 | FD194 to FD200 |
| Week 32 | FD222 to FD228 |
| Week 36 | FD250 to FD256 |
| Week 40 | FD278 to FD284 |
| Week 44 | FD306 to FD312 |
| Week 48 | FD334 to FD340 |
| Week 52 | FD362 to FD368 |
| Week 53 (Follow-up) | FUD1 to FUD7 |
| Week 54 (Follow-up) | FUD8 to FUD14 |
| Week 55 (Follow-up) | FUD15 to FUD21 |

The study week determination for the vasomotor symptoms data is based on the following:

Calculations for weeks up through Week 12 end on the last day of the study week. Calculations for weeks beyond the double-blind treatment period are centered about protocol-specified visits to match visit-based efficacy assessments. For example, the Week 12 analysis window ends on FD84 (7*12=84), but the Week 16 visit is centered around protocol specified FD113 (FD110 to FD116). Calculations in the follow-up period end on the last day of the study week, based on study days in the follow-up period.

Weeks 44, 48 and 52 will be missing for subjects randomized to placebo during the doubleblind treatment period because they are only on active treatment for 40 weeks.

A weekly average will be calculated if any information, including zero VMS events, was reported for 4 or more days.

All other efficacy assessments, including those from unscheduled visits and regardless of visit label, will be allocated to analysis visits based on the table below:

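### The Week 52 windows for C-SSRS, ECG, bone markers and TVU take in the 40-week visit of women switched from placebo; for bone markers and TVU they also take in early-discontinuation values from fezolinetant day 2

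*SAP*

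**What the plan says.** **Day count.** 52-week SAP Section 6.10.1: "Fezolinetant Study Day (FD) will be calculated as date of visit/assessment – first dose date of fezolinetant +1". A woman given placebo for 12 weeks starts this count at about study Day 85.

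**Efficacy.** For diary data, Section 6.10.1.1 draws the consequence: "Weeks 44, 48 and 52 will be missing for subjects randomized to placebo" in the double-blind period, "because they are only on active treatment for 40 weeks". The Week 52 window for visit-based efficacy measures, FD358 to FD372, agrees with that.

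**Safety.** In Section 6.10.1.2, Week 52 is FD352 to FD376 for laboratory tests, vital signs and pharmacodynamic samples. The Week 40 row reads "Week 40 | D281 | 268 to 295 | 268 to 295 | 268 to 295", with no entry for C-SSRS. Other assessments have their own Week 52 rules:

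- C-SSRS: FD268 to FD376.
- ECG: the last value from FD100 to FUD1, the day after the last dose.
- Bone markers: "The analysis window for the Week 52 bone marker is FDay 2 to FUD1".
- TVU: "The analysis window for the Week 52 TVU and biopsy assessments is FDay 2 until last treatment + 30 days".

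**Reporting.** Section 6.5 presents safety in four groups: 30 mg throughout, placebo then 30 mg, 45 mg throughout, and placebo then 45 mg. Section 6.5.5 gives means, SDs and changes for endometrial thickness and bone markers by group and visit. Biopsy is listed only.

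**Schedule.** In the protocol's Table 1, TVU is done at screening and at Visit 15/EOT/ED. Bone markers are taken at Day 1, at Visit 15/EOT/ED and at follow-up.

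**The concern.** The 52-week SAP uses fezolinetant days so that a visit label reflects time on drug. Four Week 52 windows do not keep to this. For a switched woman, the same clinic visit is Week 40 for ALT and Week 52 for ECG. C-SSRS is also inconsistent within its own column: her Day 169 assessment falls at FD85 and is labelled Week 12, which is her true exposure, while her Day 365 assessment is labelled Week 52, which is not.

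The second problem lies within each group. Bone markers and TVU are otherwise scheduled only before treatment (bone markers also at follow-up), so their Week 52 row takes whatever value was obtained at the end of treatment, however early that was. A mean headed Week 52 could then include values after days or weeks of drug.

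At stake is whether a reader can tell how many women have one-year endometrial and bone data, and whether the rows can be compared across the four columns.

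**Working it through.** **Inputs.** FD formula (52-week SAP 6.10.1); study Days 85 and 365 for the Week 12 and Week 52 visits (protocol Table 1); visit tolerance, "Subjects will return to the study site for visits and procedures to occur within ± 3 days of the scheduled day" (protocol Table 1, footnote c); windows (52-week SAP 6.10.1.2); about 20% stopping before Week 12 and 150 women per arm (12-week SAP Section 3).

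**1. Where a switched woman's last visit falls.** FD = visit day − first fezolinetant day + 1.

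- On schedule: 365 − 85 + 1 = FD281. This reproduces the SAP's Week 40 target day, D281.
- Earliest, with ±3 days at both visits: 362 − 88 + 1 = FD275.
- Latest: 368 − 82 + 1 = FD287.

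**2. FD275–287 against each window.** Earliest exposure is (first FD − 1)/7 weeks.

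| Assessment | Week 52 window | Earliest exposure accepted | Label for FD275–287 |
|---|---|---|---|
| Labs, vitals, PD | FD352–376 | 351/7 = 50.1 weeks | Week 40 (FD268–295) |
| C-SSRS | FD268–376 | 267/7 = 38.1 weeks | Week 52 |
| ECG | FD100 to FUD1 | 99/7 = 14.1 weeks | Week 52 |
| Bone markers | FD2 to FUD1 | 1/7 = 0.1 weeks | Week 52 |
| TVU | FD2 to last treatment + 30 days | 1/7 = 0.1 weeks | Week 52 |

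Every switched woman who completes on schedule, within the visit tolerance, gets the wrong label for all four assessments.

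**3. Early-discontinuation values within an active arm.**

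- *Bone markers and TVU.* Before Week 12: 0.20 × 150 = 30 women, so up to 30/150 = 20% of values come from 12 weeks of exposure or less. If a further 0–20% of the remaining 120 stop later (an assumption; the documents give no figure), that adds 0–24 women. The early-discontinuation share is then 30/150 = 20% to 54/150 = 36%.
- *ECG.* Values at FD2–99 go to Week 12. On the same assumption, with all later leavers stopping after FD99, the share is 0/120 to 24/120, or 0–20%.
- *C-SSRS.* Values at FD2–127 go to Week 12 and at FD128–267 to Week 24. The Week 52 window covers 267/7 = 38.1 to 375/7 = 53.6 weeks, so mixing within a group is limited.

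The bone-marker and TVU shares are ceilings. They assume that every leaver is assessed inside the window, and the bone-marker window closes one day after the last dose.

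**4. TVU baseline.** The Section 5 table pairs "General safety and TVU" with a Week 12 baseline for switched women. The governing rule in Sections 5 and 6.5 takes the latest available value up to the first fezolinetant dose. Table 1 schedules no TVU or bone-marker sample at Week 12, so the scheduled value is already the one from before randomization.

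**The case against.** The best defence is that the bone-marker and TVU rows are end-of-treatment rows in all but name. The protocol column is Visit 15/EOT/ED, and a wide window matches a test done once after baseline. Section 7.1 records the TVU and biopsy window as a deliberate choice, made for consistency with another study in the program. Section 6.3 tabulates exposure by group up to more than 364 days, and every summary is descriptive. This explains why the windows are wide, but it does not justify the Week 52 label. The program-consistency rationale does not mention switched women or early leavers. The exposure table describes the group, not the women behind a given TVU or bone-marker mean. The rule that picks the value closest to the scheduled day does not help when a leaver has only one value.

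Three stronger inferences are tempting, and the documents do not support them:

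- *That 40-week and 52-week women are averaged together.* Section 6.5 keeps them in separate columns, and Section 6.1 states up to 9 and up to 12 months of exposure.
- *That all four windows accept discontinuation visits from day 2.* ECG starts at FD100 and C-SSRS at FD268.
- *That the baseline entry distorts TVU change scores.* It alters no scheduled value.

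**Conclusion.** The point stands as a labelling fault in four assessments and a composition fault in two. Followed as written, the plan produces Week 52 rows that are not 52-week data.

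For switched women, all scheduled Week 52 values for C-SSRS, ECG, bone markers and TVU come from about 40 weeks of exposure or less. This follows from the SAP's own day count and needs no assumption about dropout. In the continuous arms, up to about 30 of 150 bone-marker and TVU values per arm would come from 12 weeks or less. That figure rests on the planning rate of 20% and on complete early-discontinuation assessment within the window. The upper end of the 20–36% range rests further on an assumed rate of later stopping.

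A reader might also infer that a real long-term effect on endometrium or bone is being diluted. The documents do not show this: protocol Section 1.4.2 reports no clinically meaningful change in bone turnover markers or endometrial assessments in the 12-week phase 2b study. That does not settle the question at 52 weeks, which is why the row should contain what its label says. No hypothesis test is affected. The change should be made because it is cheap and the present rows would mislead.

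**What to change.** In 52-week SAP Section 6.10.1.2 and the matching table shells:

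1. Relabel the bone-marker, TVU and ECG Week 52 rows as End of treatment/ED, and show exposure at assessment beside them.
2. Add a true Week 52 summary with lower bound FD352. Keep the existing upper bounds, including last treatment + 30 days for TVU, so that completers scanned after FD376 are not lost. A woman who stops at FD325 could still be scanned at FD355 and pass this bound, which is another reason to show exposure.
3. Label the FD268–295 visit of switched women Week 40, including for C-SSRS.
4. As a wording clean-up only, give TVU the randomization baseline in the Section 5 table, as the biopsy row already has.

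The cost is an edit to the window table, labels and shells, with no new data. The downside is fewer women under a true Week 52 label; the End of treatment/ED rows still report everyone else.
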